5.5 Depression and Suicidality

Alcohol- and opioid-dependent patients, including those taking VIVITROL, should be monitored for the development of depression or suicidal thinking. Families and caregivers of patients being treated with VIVITROL should be alerted to the need to monitor patients for the emergence of symptoms of depression or suicidality, and to report such symptoms to the patient's healthcare provider.

Alcohol Dependence

In controlled clinical trials of VIVITROL administered to adults with alcohol dependence, adverse events of a suicidal nature (suicidal ideation, suicide attempts, completed suicides) were infrequent overall, but were more common in patients treated with VIVITROL than in patients treated with placebo (1% vs 0). In some cases, the suicidal thoughts or behavior occurred after study discontinuation, but were in the context of an episode of depression that began while the patient was on study drug. Two completed suicides occurred, both involving patients treated with VIVITROL.

Depression-related events associated with premature discontinuation of study drug were also more common in patients treated with VIVITROL (~1%) than in placebo-treated patients (0).

In the 24-week, placebo-controlled pivotal trial in 624 alcohol-dependent patients, adverse events involving depressed mood were reported by 10% of patients treated with VIVITROL 380 mg, as compared to 5% of patients treated with placebo injections.

Opioid Dependence

In an open-label, long-term safety study conducted in the US, adverse events of a suicidal nature (depressed mood, suicidal ideation, suicide attempt) were reported by 5% of opioid-dependent patients treated with VIVITROL 380 mg (n=101) and 10% of opioid-dependent patients treated with oral naltrexone (n=20). In the 24-week, placebo-controlled pivotal trial that was conducted in Russia in 250 opioid-dependent patients, adverse events involving depressed mood or suicidal thinking were not reported by any patient in either treatment group (VIVITROL 380 mg or placebo).

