CTP	Participant ID	AE Description	Onset date	Severity of AE	Relatedness	Outcome	Resolution Date	AE Associated With	Preferred Term	System Organ Class

Note: MedDRA v19.0 or higher.

Table 40: Listing of Serious Adverse Events by Treatment Arm										
Treatment Arm = XR-NTX										
									MedDRA	
CTP	Participant ID	AE Description	Onset date	Severity of AE	Relatedness	Outcome	Resolution Date	AE Associated With	Preferred Term	System Organ Class

Note: MedDRA v19.0 or higher.

Table 41: Listing of Deaths by Treatment Arm						
Treatment Arm=BUP-NX						
					MedDRA	
CTP	Participant ID	AE Description	Onset date	Relatedness	Preferred Term	System Organ Class

Note: MedDRA v19.0 or higher.

Table 41: Listing of Deaths by Treatment Arm						
Treatment Arm=XR-NTX						
					MedDRA	
CTP	Participant ID	AE Description	Onset date	Relatedness	Preferred Term	System Organ Class

Note: MedDRA v19.0 or higher.

Table 42 Listing of Participants with HAM-D and/or CHRT Assessment Question Responses Indicating Potential Suicidality by Treatment Arm							
Treatment Arm = BUP-NX							
				HAM-D Assessment	CHRT Assessment		
CTP	Participant ID	Date of Assessment	Study Day	Suicide	I have been having thoughts of killing myself	I have thoughts about how I might kill myself	I have a plan to kill myself
OV Maryhaven							
FL Gateway Community Services							
PA Tarzana Treatment Centers							
NEC Stanley Street Treatment and Resources (SSTAR)							
GNY Bellevue Hospital Center							
PNW ETS/RCKC							
MA Avery Road							
SW Turquoise Lodge Hospital							
OV Maryhaven							
FL Gateway Community Services							
PA Tarzana Treatment Centers							
NEC Stanley Street Treatment and Resources (SSTAR)							
GNY Bellevue Hospital Center							
PNW ETS/RCKC							
MA Avery Road							
SW Turquoise Lodge Hospital							

Refer to figures for details regarding the color-coding.

Table 42 Listing of Participants with HAM-D and/or CHRT Assessment Question Responses Indicating Potential Suicidality by Treatment Arm							
Treatment Arm = XR-NTX							
				HAM-D Assessment	CHRT Assessment		
CTP	Participant ID	Date of Assessment	Study Day	Suicide	I have been having thoughts of killing myself	I have thoughts about how I might kill myself	I have a plan to kill myself
OV Maryhaven							
FL Gateway Community Services							
PA Tarzana Treatment Centers							
NEC Stanley Street Treatment and Resources (SSTAR)							
GNY Bellevue Hospital Center							
PNW ETS/RCKC							

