MA Avery Road							
SW Turquoise Lodge Hospital							
OV Maryhaven							
FL Gateway Community Services							
PA Tarzana Treatment Centers							
NEC Stanley Street Treatment and Resources (SSTAR)							
GNY Bellevue Hospital Center							
PNW ETS/RCKC							
MA Avery Road							
SW Turquoise Lodge Hospital							

[figure not shown]
Refer to figures for details regarding the color-coding.

Table 43: Summary of Participants with Responses Indicating Potential Suicidality by Treatment Arm			
	BUP-NX (N=)	XR-NTX (N=)	Total (N=)
Number of Participants who endorsed suicidal ideation on CHRT at Screening			
Number of Participants who endorsed suicidal ideation on CHRT at any Follow-up Visit			
Number of Participants who endorsed suicidal ideation ¹ on HAM-D ¹ at Screening			
Number of Participants who endorsed suicidal ideation on HAM-D at any Follow-up Visit			
Number of Participants who ever endorsed a suicide attempt ² on the HAM-D at any Follow-up Visit			
Number of Participants with AE's MedDRA-coded as either Suicide attempt, Suicidal Ideation, Self injurious behavior or Depression suicidal			

¹ Indicated as a response of 1 or higher to the HAM-D Suicide Question.

[figure not shown]
² Indicated as a response of 4 on the HAM-D Suicide Question

Figure 18: Participant-level Plot of HAM-D Question 3: Suicide by Treatment Arm
Figure 18A: Treatment Arm = BUP-NX

Example figure provided. The figure colors will be modified to accommodate color blind readers.

Figure 18B: Treatment Arm = XR-NTX

Example figure provided. The figure colors will be modified to accommodate color blind readers.

Figure 21: Participant-level Plot of CHRT Question 16: I have a plan to kill myself, by Treatment Arm

Figure 12A: Treatment Arm = BUP-NX

[figure not shown]
Example figure provided. The figure colors will be modified to accommodate color blind readers.

Figure 12B: Treatment Arm = XR-NTX

[figure not shown]
Example figure provided. The figure colors will be modified to accommodate color blind readers.

Figure 22: Participant-level Trajectories for Participants with Aspartate Aminotransferase > 225 IU/L by Treatment Arm

Example figure provided.

Figure 23: Participant-level Trajectories for Participants with Alanine Aminotransferase > 225 IU/L by Treatment Arm

Example figure provided.

Table 44: Listing of Liver Function Tests for ALT and AST exceeding 45 IU/L by Treatment Arm							
Treatment Arm=BUP-NX							

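### Table 43's adverse-event row omits completed suicide, and its follow-up rows cannot show new-onset suicidal ideation by arm

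*SAP*

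**What the plan says.** Table 43 (SAP Appendix A) gives counts by arm in six rows.

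- **CHRT, two rows:** "Number of Participants who endorsed suicidal ideation on CHRT at Screening" and "Number of Participants who endorsed suicidal ideation on CHRT at any Follow-up Visit".
- **HAM-D ideation, two rows:** one at screening, and "Number of Participants who endorsed suicidal ideation on HAM-D at any Follow-up Visit". The cut-off is footnoted: "Indicated as a response of 1 or higher to the HAM-D Suicide Question".
- **HAM-D suicide attempt, one row:** a response of 4 on the same item at any follow-up visit.
- **Adverse events, one row:** participants with events "MedDRA-coded as either Suicide attempt, Suicidal Ideation, Self injurious behavior or Depression suicidal".

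The adverse-event row states no time window and does not say whether it is limited to treatment-emergent events. The table does not define a follow-up visit. It has no row for participants who were negative at screening and positive later.

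Other planned outputs bear on the same question. Table 40 lists SAEs by arm. "Table 41: Listing of Deaths by Treatment Arm" carries the MedDRA preferred term for each death. Tables 34 to 36 summarise treatment-emergent events, which SAP 7.4.1 restricts to events after induction. Table 42 lists suicidality responses by participant, date and study day, and Figures 18 to 21 plot them by participant.

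**The concern.** The XR-NTX label in Protocol Appendix C, section 5.5, treats ideation, attempts and completed suicides as one group of events. It reports two completed suicides in the alcohol-dependence trials, both on drug. Table 43's adverse-event row covers that group except for its most severe member. A reader who takes Table 43 as the by-arm account of suicidality could see a lower count in an arm where a suicide had occurred.

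The same label section says patients "should be monitored for the development of depression or suicidal thinking", which is a question about emergence. Some ideation at screening is to be expected here, because SAP 1.6.2 excludes only ideation that needs immediate attention. A participant positive at screening and again later is counted in both the screening row and the follow-up row. Without a cross-tabulation, the two marginal counts do not show how much follow-up ideation is new.

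**Working it through.** The documents give no rate, power or sample size for suicidality, so there is no stated figure to reproduce. The check is a reading of the rows, followed by an illustration.

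**1. Where a suicide death would appear.** Take a participant who dies by suicide with no earlier positive CHRT or HAM-D response and no event coded to the four terms.

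- Table 43: no row.
- Tables 40 and 41: listed by arm with preferred term, whether or not the participant was inducted.
- Table 34: counted under Death without cause, only if treatment-emergent.
- Tables 35 and 36: a preferred-term row, only if treatment-emergent.

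For a randomized but never-inducted participant, the death would therefore appear only in the listings. Protocol 9.2 expects successful induction to be less frequent on XR-NTX, so that situation may not be equally common in the two arms.

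**2. Size of one omission.** With about 300 per arm (Protocol 12.2), one participant is 1/300 = 0.33 percentage points.

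**3. What the follow-up rows count.** Positive at screening only: screening row only. Positive at screening and later: both rows. Negative at screening and positive later: follow-up row only. The follow-up row is the sum of the last two groups.

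**4. Illustration of the mixing (all rates assumed).** Let *s* be the share positive at screening, *r* the share of those positive again at follow-up, and *n* the new-onset rate among those negative at screening. Take *s* and *r* equal in both arms.

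Follow-up row = *s* × *r* + (1 − *s*) × *n*

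With *n* = 4% and 8%, the new-onset ratio is 2.0 and the difference is 4.0 points.

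| *s* | *r* | Arm with *n* = 4% | Arm with *n* = 8% | Ratio | Difference |
|---|---|---|---|---|---|
| 0.10 | 0.4 | 0.040 + 0.036 = 7.6% | 0.040 + 0.072 = 11.2% | 1.47 | 3.6 |
| 0.10 | 0.6 | 0.060 + 0.036 = 9.6% | 0.060 + 0.072 = 13.2% | 1.38 | 3.6 |
| 0.20 | 0.4 | 0.080 + 0.032 = 11.2% | 0.080 + 0.064 = 14.4% | 1.29 | 3.2 |
| 0.20 | 0.6 | 0.120 + 0.032 = 15.2% | 0.120 + 0.064 = 18.4% | 1.21 | 3.2 |

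The difference in the row is (1 − *s*) × 4.0 points whatever *r* is, so it moves little. The ratio moves more.

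**5. Unequal persistence.** With *s* = 0.20 and *n* = 4% in both arms, but *r* = 0.4 in one and 0.6 in the other, the rows read 11.2% and 15.2%. That is a 4.0-point difference with no difference in new onset. The row alone cannot distinguish this from the situation in step 4.

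**The case against.** The strongest reply is that nothing is lost from the reporting. Table 43 is titled as a summary of responses, with one adverse-event row attached. Every death is listed by arm with its coded term, and SAP 7.4.1 plans by-arm summaries and tests of adverse events by type. New onset can be worked out from Table 42 and the participant-level figures. This stands. A reader might infer that the SAP misses suicide altogether, and the documents do not support that: the gap is confined to one table.

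A reader might also infer that ideation seen only at screening is carried into the follow-up rows. It is not, because those rows require a positive response at a follow-up visit.

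Total follow-up ideation by randomized arm is itself a legitimate comparison. Randomization should balance screening ideation, and a treatment may relieve or prolong it. This also stands, and it is why the existing rows should stay. It does not remove the case for showing new onset beside them.

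The label's opioid data are less worrying than its alcohol data. No depressed-mood or suicidal-thinking events were reported in either arm of the 250-patient placebo-controlled trial. In the open-label study, events of a suicidal nature were 5% on XR-NTX and 10% on oral naltrexone. The alcohol-trial figure of 1% against 0 therefore cannot be carried over as an expected rate.

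Finally, the four terms match the suicidality and self-injury terms in the shells of Tables 35 and 36, so the list may have been taken from events already coded. That is plausible but unproven, and a fixed list would still fail to pick up a term coded later.

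**Conclusion.** The point holds as a minor gap in one safety table. Table 43 would omit a suicide death that came without another listed event or positive response, and it cannot show new-onset ideation by arm. Both facts follow from the row wording and need no assumption.

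The size is uncertain. One omitted suicide is 0.33 points at about 300 per arm, and the documents give no basis for expecting any particular number. The ratios of 1.21 to 1.47 rest on assumed screening, persistence and new-onset rates, with persistence taken as equal in the arms. On the difference scale the effect is slight (4.0 to 3.2–3.6 points).

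A reader might infer that a formal arm comparison is biased or underpowered. The SAP specifies no test for Table 43, so the comparison is a descriptive side-by-side and power is not at issue. The primary analysis is unaffected.

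**What to change.** In SAP Appendix A, Table 43:

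1. Add *Completed suicide* to the adverse-event row and state the row's time window, including whether it is limited to treatment-emergent events.
2. For CHRT and for HAM-D item 3, add a descriptive by-arm row counting participants negative at screening who are positive at any post-randomization visit. The denominator is participants negative at screening with at least one post-randomization assessment on that instrument. This wording also avoids the undefined term for follow-up visits.
3. Keep the existing rows.

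Do not add adjudication of whether overdoses were intentional. It would bring subjective judgement into an open-label trial, and Overdose already has its own preferred-term row in Tables 35 and 36.

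The cost is shell wording and a few lines of programming on data already collected. The new denominator does not equalise the number of assessments per participant. Relapse ends weekly research visits and medical management (Protocol 10.1 and 11.3.2), so a footnote giving assessments per participant by arm would help the reader.
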